Protocol Title: Thermalogical Analysis of a cohort of women undergoing mammographic analysis.

Protocol Number: SBS-001

Version Number: 1

Version Date: 6/28/2017

Contact Information

Principal Investigator

[name]
University of Toledo
[name]
[contact]
E-mail:[contact]

Study Sponsor

[name] CEO
First Sense Medical, LLC
[name]
[contact]
Email: [contact]

Clinical Research Coordinator

[name]
Eleanor N. Dana Cancer Center
[name]
[name]
[contact]
Email: [contact]

Proprietary and Confidential

The information in this document is considered privileged and confidential, and may not be disclosed to others except to the extent necessary to obtain Institutional Review Board approval and informed consent, or as required by Federal and State laws. Persons to whom this information is disclosed should be informed that this information is privileged and confidential and that it should not be further disclosed.

Protocol Signature Page

Protocol No: SBS-001

Version Date: 6/28/2017

1. I agree to follow this protocol version as approved by Schulman and Associates IRB.
2. I will conduct the study in accordance with applicable IRB requirements, Federal regulations, and state and local laws to maintain the protection of the rights and welfare of study participants.
3. I certify that I, and the study staff, have received the requisite training to conduct this research protocol.
4. I have read and understand the information in the Investigators' Instructions for Use regarding the risks and potential benefits. I agree to conduct the protocol in accordance with Good Clinical Practices (ICH-GCP), the applicable ethical principles, the Statement of Investigator (Form FDA 1572), and with local regulatory requirements.
5. I agree to maintain adequate and accurate records in accordance with IRB policies, Federal, state and local laws and regulations.

[figure not shown]
University of Toledo Principal Investigator

Printed Name

Signature

Date

Study Schema

SBS II: positive for TH 4 and 5, negative for TH 0, 1, 2, 3, or 6

mammogram: negative for BIRADS 1 and 2, positive for BIRADS 0, 3, 4, 5, or 6

List of Abbreviations

CBE	Clinical Breast Exam
FSM	First Sense Medical®, LLC
SBSII	Sentinel Breast Scanner
TS	Therma-Scan Reference Laboratory, LLC (analyzes and produces report)
FS/TS	First Sense/Therma-Scan
MMG	Mammogram
PPV	Positive Predictive Value
PI	Principal Investigator
IRB	Institutional Review Board

Introduction

First Sense Medical®, LLC is a medical device company which has developed a breast cancer screening device, the Sentinel Breast Scan II [SBSII]. This radiation free device is being developed to produce data which will be analyzed by Therma-Scan Reference Laboratory. [name], CEO of Therma-Scan, is the author of a published paper based on breast thermal data with a reported 95% sensitivity and 91% specificity¹. The SBSII examination will take approximately 7 minutes.

This study is designed to evaluate the Sentinel Breast Scan II® as well as the analysis of data by Therma-Scan. SBSII® thermal breast data is an adjunctive aid to standard breast imaging. Currently, mammography is one of the standards of care in screening for visible signs of breast cancer. Breast thermology is the analysis of the heat signature data from an examined breast. All study costs will be incurred by the sponsor. Study subjects will incur no cost to participate. All scientific data revealed in this protocol will be used for the specific objectives of the study. The SBSII is a non-significant risk device. There is no contact with the subject during the entire procedure.

Background Information

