1.2 Therma-Scan System

First Sense Medical® has partnered with Therma-Scan Reference laboratory, an established pioneer in medical thermology. Therma-Scan has been in operation for over 40 years and operates a diagnostic clinical imaging facility in Birmingham, Michigan. [name] has developed a complex and inclusive protocol for the detection of tissue abnormalities indicative of Breast Cancer. He has examined thermology scans on more than 500,000 women using a medical grade digital infrared camera

¹Hoekstra P, The autonomic challenge and analytic breast thermology. *Thermology International*, 2004(14);3:106.

²[American Cancer Society](#)

that utilizes advanced imaging techniques. [name] follows an analytic technique derived from the Marseille system to provide results of a breast thermogram on a recognized 'TH' scale.

Breast thermology is effective on women of all ages. And the density of breast tissue is not an impediment to breast thermal analysis. Utilization of the Marseille system, an internationally standardized thermology classification system, defines 5 TH categories based on a range of breast thermal findings; these range from TH-1, considered normal, thru TH-5, considered abnormal. Additionally, there are two other categories: TH-0, a technically defective test and TH-6, a known biopsy proven cancer. Therma-Scan Reference Laboratory will screen for thermal signs indicative of change and report the findings using this proven system.

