1.3 Sentinel Breast Scan® System [SBSII]

The SBSII will automate the recording of thermal data used in the Therma-Scan manual thermology protocol by utilizing a thermal camera sensitive to changes in breast temperature. The SBSII system uses a very sensitive thermography camera that detects and visually displays heat patterns that naturally emanate from the breast. SBSII captures this data digitally for subsequent analysis by Therma-Scan.

This study will evaluate the clinical efficacy of the SBSII device in patients completing a screening or diagnostic mammogram. The thermal images captured on examination will be analyzed by Therma-Scan and the results will be compared to mammographic analysis. If the Sentinel Breast Scan II findings indicate a reading of either TH4 or TH5, FSM may request that the patient receive additional testing, ie breast ultrasound or MRI. The additional testing that are not considered routine and necessary based on standard breast imaging, will be paid for by the sponsor, as outlined in the study budget.

1.3.1 Projected Advantages of Sentinel Breast Scan® Test/Therma-Scan System:

1. **Higher sensitivity and positive predictive value (PPV)**, Sensitivity measures the percentage of positive results when cancer is present. PPV is the true positive rate, and is the percentage of abnormalities with a positive result. The false positive rate is the percentage of normals identified as abnormal. Higher positive sensitivity in a screened population is the goal of all screening methods. This parameter will be utilized in the analysis of data from this study.
2. On average, mammographic **sensitivity** varies between 60-90%. It is lower in women under age 40 and in those with dense breast tissue.
3. **Year-to-year comparisons.** An important factor in analysis is identification of subtle visual change that is detected by comparing a previous mammogram to a current one. SBSII® seeks to identify subtle changes over time in breast thermal signals through the use of sophisticated software.
4. **Patient Safety:** Practice guidelines in the United States delay screening younger women with mammography based on the accretion rate of radiation exposure. Thermographic analysis of the breast is radiation free and innocuous as a screening modality for younger women and is not affected by breast density.

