5. **Greater Access.** Because breast thermography can be performed in a non shielded environment, the opportunity to use this technology in a more welcoming environment is apparent.

Objectives/Purpose

The primary objectives of this feasibility study are to evaluate the functionality and performance of a novel adjunctive breast cancer screening system (FSM SBSII/Therma-Scan System) and utilize the data to provide further calibration for system software.

Specific Objective 1: To observe and document the performance of the FSM SBSII automated imaging system hardware and software in a clinical setting, and analysis of that data by TS.

Specific Objective 2: To both modify [if indicated] and measure the accuracy of an established manual thermographic analytical protocol (performed by TS), as well as define the approximate location of a particular finding and classify thermal irregularities in breast tissue.

Specific Objective 3: To develop and measure the accuracy of the system software to both approximate the geographic location of and classification of thermal change in breast tissue.

Thermal imaging captures the intensity and patterns of skin temperature using a high-performance infrared (8-14 μ m wavelength) camera. Pre-cancerous and cancerous breast tissue results in regional heating of the skin accompanied by complex irregularities in vascular patterns and aberrations in the adaptive modulation of skin temperatures³. This information can be imaged by thermal cameras and will be analyzed by TS. Although thermography cameras have been approved by the FDA for adjunctive use in breast cancer screening, this technology has not been widely accepted for several critical reasons. Lack of adequate quality control, adherence to standards for experience and training and inconsistency from practitioner-to-practitioner in the application of this technology have resulted in published studies with wide ranging sensitivity and specificity (Fitzgerald and Berentson-Shaw 2012). Because of this clinicians have been prevented from formulating a reasoned conclusion about the efficacy of breast thermography as adjunctive to standard breast imaging or its value as a method of risk assessment. Peer-reviewed clinical studies have amassed thousands of subjects and data points over time. However, a scarcity of systematic review and meta-analysis has impeded meaningful comparison to standard breast imaging technology (Vreugdenburg, Willis et al. 2013).

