The core strengths of thermography are multi-faceted. Thermography is a fast, non-invasive, low cost and painless procedure performed without radiation exposure. Published studies support its use for early detection of breast tissue abnormalities and in identifying groups that may be at higher risk for developing breast cancer.

As an adjunct to mammography, thermography may be especially useful for screening younger, pre-menopausal women and women with dense breast tissue for whom mammography is less effective (Bleyer and Welch 2012).

³ Library, T.-S. R. (2011). "Thermology: Analytic Features." [A Professional's Guide To Breast Thermology](http://www.thermascan.com/professionals.html)
Retrieved January 4, 2013, from <http://www.thermascan.com/professionals.html>.

An automated platform for collecting thermal imaging data that provides objective, interpretative guidelines and standardized reporting would be an important adjunctive tool to aid in risk assessment and clinical decision-making in breast cancer screening.

Study Design and Selection and Exclusion of Subjects

1.4 Study Design: Testing a minimum of 2000 women receiving mammograms (comparing the SBSII/TS test results to the mammogram and biopsy results when applicable)

- a. SBSII test will be done before all mammograms, diagnostic or screening
- b. Women must wait a minimum of (3) days between mammography and the SBSII.
- c. If the SBSII test is positive and mammography is negative, FirstSense may request a breast ultrasound or MRI to determine the accuracy of SBSII. The acquisition order for MRI study will be done with prior approval by FSM.
- d. Any study subject, regardless of biopsy diagnosis and treatment, will continue to complete the SBS II imaging in conjunction with all future routine and necessary mammograms, not to exceed less than 6 months between each SBS II imaging, for up to 5 years from the start date of the subject's study participation. For subjects that undergo mastectomy after initial study participation, and are no longer completing routine and necessary mammograms, the SBS II will be completed with future routine and necessary breast MRI imaging, not to exceed less than 6 months between each SBS II imaging, for up to 5 years from the start date of the subject's study participation.

1.4.1 Subject Inclusion Criteria:

1. Female, over the age of 18 years of age.
2. Asymptomatic women or women who are being screened for breast abnormality.

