With the subject properly positioned in front of the SBSII scanner, the study staff will inform the subject that the test will take approximately 7 minutes and that there will be no physical contact with the tester. The participant will be advised to remain still during the scanning process.

Before thermal image acquisition, the SBS II study staff operator will determine the frontal and lateral thermal image acquisition angles using the live thermal image of the subject’s breasts provided on the SBSII monitor. Once the angles are determined, the study staff operator will start the test. During the first step the patient will acclimate for 30 seconds, then cool air will be blown on the breasts for approximately 3 minutes. The air is then stopped and the patient will then acclimate for approximately 3 minutes. Thermal images are acquired starting at the first step and continuously until after the final acclimation step is completed. The patient must remain motionless throughout the initial period of acclimation, during the cool air sequence, and the final acclimation sequence in order to capture thermal images in series from the start of the test to its completion.

End of the test:

The test will be completed when the SBSII scanner signals that all images are acquired. The patient is now allowed to move.

Assessment of Safety and Risk

The potential risks are identified in this study and tests have been done to mitigate the risk.

Table 2. Risk Assessment

Medical Risk	Initial Severity	Initial Frequency	Control Measures	Final Severity	Final Frequency
Blowing cold air onto participants may cause discomfort.	Low	Remote	Participants may leave the study any time during a test.	Minor	Remote

Mix a patient's results with another patient.	Low	Remote	Each participant will be assigned a unique study ID. This ID will be entered electronically through the SBS II Tester User interface. This ID will be appended to the Thermal Data file names. Patients will not receive final reports.	Minor	None
---	-----	--------	---	-------	------

Discontinuation of the Study

At any time before or during the SBSII test, a subject is able to cancel or discontinue the clinical trial without penalty.

Data Analysis

1.5 Data analysis for Specific Objective 1:

The system hardware and software will be observed and log files will be analyzed by FSM to confirm proper operation of the system.

1.6 Data analysis for Specific Objective 2:

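### The Study Schema, the protocol's only definition of a negative SBSII test, includes defective scans (TH-0) and known cancers (TH-6); the accuracy table in 1.6 needs its own rule

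*Protocol*

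**What the plan says.** The Study Schema at the front of the protocol gives one line for each test. The SBSII line is "SBS II: positive for TH 4 and 5, negative for TH 0, 1, 2, 3, or 6". The mammogram line sorts the BI-RADS categories into negative and positive in the same way.

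Section 1.2 describes five TH categories, from normal (TH-1) to abnormal (TH-5), and then adds: "Additionally, there are two other categories: TH-0, a technically defective test and TH-6, a known biopsy proven cancer".

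Section 1.6 (analysis for Specific Objective 2) also speaks of five risk categories and has the reading end in a class from TH-1 to TH-5. Its two-by-two table has one row for a positive and one for a negative test. It attaches no TH values to either row and mentions neither TH-0 nor TH-6.

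Elsewhere the TH 4-5 cut appears only as a trigger for action. Section 1.3 says "If the Sentinel Breast Scan II findings indicate a reading of either TH4 or TH5, FSM may request that the patient receive additional testing", and 1.6 has a similar sentence about a recommendation from the sponsor. Section 1.4, item c, uses the words positive and negative without TH values: "If the SBSII test is positive and mammography is negative, FirstSense may request a breast ultrasound or MRI". It gives the purpose of that imaging as determining how accurate the SBSII is.

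**The concern.** A scan that failed technically carries no reading. If it is entered as a negative result, the table credits or debits the test for something it did not do. In a woman with cancer the failure is counted as a miss. In a woman without cancer it is counted as a correct negative. The result is neither accuracy among readable scans nor a worst case, because failures count against sensitivity and in favour of specificity.

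Sensitivity and specificity are the measures that 1.6 names for Specific Objective 2. Mixing failures with readings would make it impossible to tell a misread from a failed acquisition. It would also hide a figure that Specific Objective 1 could use, since that objective is "To observe and document the performance of the FSM SBSII automated imaging system hardware and software in a clinical setting".

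The TH-6 coding is a secondary matter. Section 1.4, item d, states: "Any study subject, regardless of biopsy diagnosis and treatment, will continue to complete the SBS II imaging". Exams of women with an already proven cancer can therefore occur, and the schema would label them negative.

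**Working it through.** **Step 1. Which passages agree.**

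| Place | TH-0 | TH 1-3 | TH 4-5 | TH-6 |
|---|---|---|---|---|
| Study Schema | negative | negative | positive | negative |
| 1.2 | separate code: failed test | risk scale | risk scale | separate code: known cancer |
| 1.6 text | not mentioned | risk scale | risk scale; may prompt a recommendation | not mentioned |
| 1.6 table | no row | not mapped | not mapped | no row |

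Sections 1.2 and 1.6 are consistent: five risk categories, with two further codes outside them. The schema alone treats those two codes as test results. It is also the only place that says which categories are negative.

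**Step 2. Can TH-0 occur?** The protocol has a code for it, so it is foreseen. The end-of-test rule, "The test will be completed when the SBSII scanner signals that all images are acquired", confirms acquisition only, not that the woman kept still as the test procedure requires. This says nothing about how often scans fail, and the protocol gives no TH-0 rate.

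**Step 3. Effect per failed scan, with no rate assumed.** Inputs: the Introduction's "reported 95% sensitivity and 91% specificity" for the manual method, and up to 45 biopsy-proven cancers in the final blinded phase (1.6). With k failed scans among 45 cancers, all coded negative:

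expected sensitivity = 0.95 × (45 − k)/45, a drop of 0.95 × k/45.

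- k = 1: 92.9%, drop 2.1 points
- k = 2: 90.8%, drop 4.2 points
- k = 3: 88.7%, drop 6.3 points

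In whole counts with one failed scan: 42 of 44 readable scans is 95.5%, but 42 of 45 is 93.3%. If true sensitivity were 80%, the drop per scan would be 0.80/45 = 1.8 points.

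**Step 4. Illustration with an assumed rate.** Let t be the TH-0 rate, equal in women with and without cancer. The values of t are assumptions.

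- Schema coding: sensitivity = 0.95(1 − t); specificity = 0.91(1 − t) + t.
- TH-0 left out: 95% and 91%.
- TH-0 wrong in both columns: sensitivity = 0.95(1 − t); specificity = 0.91(1 − t).

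| t | Sensitivity, schema | Specificity, schema | Specificity, TH-0 wrong |
|---|---|---|---|
| 2% | 93.10% | 91.18% | 89.18% |
| 5% | 90.25% | 91.45% | 86.45% |
| 10% | 85.50% | 91.90% | 81.90% |

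Compared with leaving TH-0 out, the schema coding lowers sensitivity by 0.95t (1.9, 4.75 and 9.5 points) and raises specificity by 0.09t (0.18, 0.45 and 0.90 points). The positive predictive value does not change, because true and false positives shrink by the same factor.

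**Step 5. Against sampling error.** Standard error of sensitivity = √(0.95 × 0.05/45) = 3.2 points. The shift 0.95t reaches one standard error at t = 0.0325/0.95 = 3.4%. It reaches the 95% half-width, 1.96 × 3.25 = 6.4 points, at t of about 6.7%.

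**Step 6. Cost of leaving TH-0 out.** Expected evaluable cancers = 45(1 − t): 44.1, 42.75 and 40.5 at the three rates.

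**The case against.** The strongest reply is that the schema is a key for selecting women for additional imaging, not an analysis rule. It pairs an SBSII line with a mammogram line, and 1.4 item c acts on exactly that pair. Under this reading a failed scan or a known cancer simply does not prompt sponsor-requested imaging, and placing BI-RADS 0 and 6 on the positive side makes sense too. Read literally, 1.6 admits only TH 1-5, so TH-0 and TH-6 would never enter the table. This reading is plausible and stands as a possibility. The protocol does not state it, however. Item c uses the same positive and negative terms in order to judge accuracy, and whoever fills the negative row of the table has no other definition in the protocol to use.

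A second reply is that unreadable scans belong in the SAP, which may exist. That is fair for the detail of reporting, but the point does not rest on an omission: the protocol states that a defective test is negative.

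A third is that counting a failed scan as not positive reflects use in practice and is conservative. It is conservative for sensitivity only; specificity gains from each failure.

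Stronger readings are tempting but not supported:

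- A reader might infer that the protocol contradicts itself throughout on the TH scale. It does not; 1.2 and 1.6 match.
- A reader might infer that the accuracy results will certainly be biased. That needs a link from schema to table that is not written, and a failure rate that is not given.
- A reader might infer a large effect of TH-6. The protocol gives no count of such exams, and they are probably rare in the blinded phases, so no size is claimed.
- A reader might infer that the schema distorts the accuracy of mammography. Nothing here shows that.

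**Conclusion.** The point holds as a modest one that should be fixed. The schema is the only definition of a negative SBSII test in the protocol, and it includes a code for failed scans and a code for known cancer that 1.2 and 1.6 keep apart from the risk reading. Whether it reaches the accuracy table is left open.

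If it does, the size is about 2.1 points of sensitivity for each failed scan among 45 cancers, with a small rise in specificity. This assumes the cited 95% sensitivity and the full 45 cancers; with fewer cancers each failed scan weighs more. How many such scans there will be is unknown. At TH-0 rates below about 3.4% the shift is under one standard error, although it always goes in the same direction. The stakes are limited: this is a feasibility study, and the section on intended use confines the results to device development and rules out a marketing submission.

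**What to change.** In 1.6, state that for the accuracy table SBSII positive means TH 4-5 and negative means TH 1-3. Report TH-0 separately as a count and rate of technical failure, which also serves Specific Objective 1. Add a check that counts TH-0 as wrong in both columns, so that leaving failures out does not by itself flatter the result. Keep exams of cancers already proven by biopsy (TH-6) out of the accuracy table. If the schema lines serve only to select women for additional imaging, say so beside them. This concerns the accuracy table alone and implies nothing about who should have additional imaging.

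The cost is one wording change in the schema and a few sentences in 1.6. The downside is slightly smaller denominators and a failure rate that becomes visible.

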1.1 Breast Cancer Screening Today

Screening is testing of asymptomatic (without symptoms) and symptomatic women. Mammograms identify abnormalities and determine their location in the breast. If a biopsy of the area in question is positive, treatment includes surgical removal of the cancer followed by radiation and medical therapy, if indicated. The standard protocol in the United States for Breast Cancer screening includes an annual clinical breast exam and mammogram for women over 40 years of age². Women with a family history of Breast Cancer or other indicators may be screened at an earlier age and more frequently. If the results are positive, further diagnostic testing may be prescribed and a biopsy may be taken. If the SBSII scan reveals a thermal pattern on analysis that meets established criteria and the mammogram is read as normal, FSM intends to contact the site PI. The study participant will then be encouraged to undergo additional standard diagnostic imaging tests. These additional tests are performed to assure that the patient has no evidence of abnormality utilizing advanced breast imaging techniques in use today. However, the additional tests ordered may indicate the need for further investigation prescribed by the study doctor. These imaging tests will be paid for by First Sense Medical.

